3.2. Study methodology

The study involves two screening moments (one screening questionnaire/interview to complete at home and one screening visit) followed by enrolment onto a 9-week randomized, placebo-controlled, cross-over intervention study. Each intervention period will be preceded by one week run-in period and separated by one week wash-out period in which participants will consume an average UK diet, low in plant foods. During the three 14-day intervention periods, participants will consume an average UK diet with increased amounts (8 servings per day) of specific types of fruits and vegetables (**Table 1**) or low in fruits and vegetables (control group, ≤ 2 servings per day). The diets will be fully controlled, provided by the researchers and delivered at the participants' home once a week. Participants will be involved for 9 weeks in total and will be invited to attend the Cambridge Epidemiology & Clinical Trials Unit testing sites 7 times in total.

Screening questionnaire/interview (15 minutes)

Consent/Screening visit (clinic visit, 2 hours)

Week 1: Run-in period

Week 2-3: 14-day dietary intervention

Week 4: Wash-out period

Week 5-6: 14-day dietary intervention

Week 7: Wash-out period

Week 8-9: 14-day dietary intervention

Screening questionnaire/interview (15 min)

Respondents will be sent by mail a screening questionnaire. Participants will be invited to complete and to return the screening questionnaire in the provided envelope to the researchers. If preferred, respondents can be contacted by telephone to assess suitability. The researchers will assess eligibility using the returned questionnaires and will contact all respondents by telephone to inform them if eligible. Eligible respondents will be sent the patient information sheet. Having read the information sheet, those who wish to continue the enrolment process will be invited to attend the Cambridge Epidemiology & Clinical Trials Unit testing sites for a consent visit and to continue screening.

Consent/screening visit (clinic, 2 hours)

Potential participants will be asked to visit the Cambridge Epidemiology & Clinical Trials Unit testing sites. The respondent will receive detailed information of the study protocol and their eligibility before obtaining informed consent. Questions and concerns will be discussed with the researchers before giving formal consent. Potential participants will then be eligible to continue the screening process.

Potential participants will be asked to complete a general health and lifestyle questionnaire. Automated office BP (twice with >30 min apart), anthropometrics and body composition will be measured. If eligibility criteria are met, the participant will be enrolled and randomly allocated to one of the intervention sequences. The participant will be asked to complete food diaries for 3 days (2 week and 1 weekend days) and a salt intake questionnaire to assess habitual dietary patterns and to return to the researcher by post for analyses. In the event of any abnormalities of test results, the participant will be informed and will be advised to discuss with their GP.

3.3. Dietary intervention

[figure not shown]

Figure 1: Schematic representation of the study design and clinic visits

The dietary interventions will be based on an average UK diet with similar macronutrient content:

- Control group:** 1 portion of fruits plus 1 portion of vegetables, of commonly consumed types per day. Intakes are at 25th percentile of UK consumption (NDNS) and will exclude citrus fruits, cruciferous and allium vegetables.
- Treatment 1:** 4 portions of fruits plus 4 portions of vegetables, of commonly consumed types per day excluding citrus fruits, cruciferous and allium vegetables.
- Treatment 2:** 4 portions of citrus fruits plus 4 portions of cruciferous vegetables per day.

The control group and treatment 1 will be provided with similar types of fruits and vegetables, but in different amounts, to investigate the importance of amount consumed (**Table 1**). Treatment 3 contains citrus fruits and cruciferous vegetables to test the importance of targeted types of fruits and vegetables consumed. Numbers of fruit and vegetable portions for the treatment groups are according to recommendations of the Dietary Approach to Stop Hypertension (DASH) diet.¹ Fruits and vegetables will be provided as snack, salad, cooked in mixed dishes, as 100% juice, or as soup. Allium vegetables (onion, garlic, leek, etc) will be restricted throughout the study as these vegetables also contain SMSCO. Also any other fruit or vegetable containing food will be restricted e.g., jam and fruit cakes. The diets will be matched for servings of other food groups and macronutrient balance according to average UK habitual diet. Duplicates of daily provided diets will be collected to analyse average nutritional compositions of the diet.

Meals and snacks covering 90% of daily energy needs will be delivered once a week at the participants' home according to a weekly menu cycle for each intervention sequence and accompanied by daily menus. Each day, 10% of the calorie intake is free for the participant to choose from a list of food or beverage options (to be provided by participant). This may include a maximum of one daily unit of alcohol, equalling 10 to 15 gram of ethanol. A run-in period (control diet) is to minimize the effect of habitual diet intake

before start of intervention, washout period (control diet) precedes each intervention sequence to ensure that potential cardiometabolic effects of previous diet or treatment are eliminated.

Table 1. Types of fruits and vegetables provided in each intervention sequence

Control & Treatment 1	Treatment 2
Common fruits	Citrus fruits (Rutaceae)
Apple	Clementine
Banana	Grapefruit
Grape	Lemon
Pear	Lime
	Mandarin
	Orange
Common vegetables	Tangerine
Carrot	Cruciferous (Brassicaceae Oleracea) vegetables
Cucumber	Broccoli
Sweet pepper	Brussels sprouts
Tomato	Cabbages, including savoy, white and red
	Cauliflower
	Collard greens
	Kale
	Kohlrabi

Diet control for weight maintenance is a crucial part throughout this study. Diets will be tailored to individuals' energy requirements measured by bioelectrical impedance analysis and the validated Mifflin-St Jeor equation that estimates basal metabolic rate.³¹ Body weight and appetite profiles will be measured at start and end of each intervention sequence to check weight maintenance and feelings of hunger and satiation. Menu cycles at various caloric levels will be developed, and if needed, to match energy expenditure to maintain body weight. Participants will be asked to maintain usual lifestyle habits including physical activity levels throughout the study. Participants will be asked to complete a validated questionnaire at each visit to measure any changes in physical activity. The researchers will have weekly telephone contact with participants to discuss issues relative to the provided diet or if any lifestyle changes.

Compliance to dietary intervention

To aid compliance, all meals and snacks will be delivered on a weekly basis to participant's home accompanied by instructions, daily menus and food checklists. The participant will be asked to complete the food checklists daily to report compliance to the intervention diet, the food choice for the remaining 10% kcal, and any additional foods consumed not provided by the study. Participants will be asked to return the completed checklist and uneaten foods at the next clinic visit. Compliance will also be checked with objective established and novel dietary biomarkers.

3.3. Study measurements

Participants will be invited to attend the Cambridge Epidemiology & Clinical Trials Unit testing sites for clinical measurements at days 1 and 15 of each intervention sequence having fasted from 10 pm the previous day. Participants will be provided with containers and instructions for urine and stool sample collection. At each clinic visit, participant will bring 24 hour urine and a stool samples that were collected on the previous day, as well as completed food checklists and a questionnaire reporting any medications or dietary supplements used during the specimen collection. The participants will be reminded by text message to complete these collections and questionnaires.

At arrival, a fasting venous blood sample will be taken with a volume that will not exceed 26 ml (156 ml for the whole study: see overview of fractions of blood samples in Table 3). Participants will be asked to void a spot urine for dipstick analyses to check pathological changes in the urine. Automated office BP, pulse wave

velocity, anthropometrics and body composition will be measured. Breakfast will be provided after completion of the measurements. Cognitive test will be completed at the laptop after breakfast which requires 12 to 15 minutes. We will use the same cognitive tests as currently used for the Airwave Health Monitoring study (MREC/13/NW/0588). 24-hr ambulatory blood pressure devices and AX3 accelerometers became available at a later stage of the study. Therefore, these measurements will be conducted in a subsample of participants with main aim to validate the office blood pressure measurements and subjective physical activity questionnaire data. A subsample of the CIRCUS study participants will be invited to wear a 24-hr ambulatory blood pressure monitoring device at each visit and an accelerometer throughout the study period while performing their routine work and daily activities. The 24-hr ambulatory blood pressure monitoring device is worn around the waist which is connected with a wire to the cuff along the upper arm. The accelerometer is worn around the wrist as a watch. For the 24-hr ambulatory blood pressure measurement, participants will be trained to install the device themselves or will briefly attend the clinic the day before the actual clinic visit to have the device fitted by a trained researcher. After being notified by the device with a minimum inflation of the cuff, the device will automatically start measurement of blood pressure every 30/60 minutes for 24 hours. Participants who are willing to wear the accelerometer will be fitted or replaced the wrist band at each visit by a trained researcher.

Table 2. Summary of assessments

Assessment	Screening 1	Intervention period 1		Intervention period 2		Intervention period 3		Total
	Visit 1	Visit 2	Visit 3	Visit 4	Visit 5	Visit 6	Visit 7	
Informed consent	X							1x
Screening questionnaire	X							1x
Health & lifestyle questionnaire	X							1x
Salt questionnaire	X						X	2x
Food diaries	X							3x
Anthropometrics	X	X	X	X	X	X	X	7x
Bioelectrical impedance	X	X	X	X	X	X	X	7x
Blood pressure	2x	X	X	X	X	X	X	8x
Pulse Wave Velocity		X	X	X	X	X	X	6x
Fasting blood sample		X	X	X	X	X	X	6x
24-hr urine		X	X	X	X	X	X	6x
Spot urine & dipstick test		X	X	X	X	X	X	6x
Faeces sample		X	X	X	X	X	X	6x
Cognitive tests		X	X	X	X	X	X	6x
Questionnaire including physical activity, dietary behaviour and appetite		X	X	X	X	X	X	6x

Table 3. Summary of blood samples

Blood sample	Quantity	Vacutainer	Purpose
Serum Separator Tube (SST)	6 mL	Red	Serum for biochemistry, metabolomics
Serum Separator Tube (SST)	5 mL	Gold	Serum for lipid profiles, hs-CRP, insulin
Lithium Heparine	6 mL	Green	Plasma for nutritional biochemistry (Vit C)
Fluoride Oxalate	2 mL	Grey	For glucose
EDTA	6 mL	Purple	Plasma and buffy coat for haematology and HbA1C
Total blood sample	25 mL		

At the end of the study, collected samples will be kept in locked freezer storage managed by the MRC Epidemiology Unit which hosts the Cambridge Epidemiology & Clinical Trials Unit.

4. PARTICIPANT ENTRY

4.1. Recruitment of participants

We envisage that we will need to screen many people to find 36 eligible prehypertensive participants willing to participate in this study. We will therefore use various ways to recruit respondents:

- by contacting the general pool of volunteers registered at the NIHR/Wellcome Clinical Research Facility and the Imperial College London, Division of Nutrition, and those registered at the Cambridge Epidemiology & Clinical Trials Unit of the MRC Epidemiology Unit, who participated in previous studies and who gave consent to re-contact
- by advertisement, e.g. posters and online media, in staff rooms of wards, common areas, and waiting rooms of all the trust hospitals (Charing Cross, Hammersmith, and St Mary's hospitals), and Addenbrookes Hospital in Cambridge, Prince of Wales Hospital in Ely, North Cambridgeshire Hospital in Wisbech and Imperial College London/University of Cambridge campuses – and via staff newsletters.
- by contacting participants of the Airwave Health Monitoring Study who consented to be approached for recruitment of subsequent studies. The Airwave Study is an epidemiological occupational cohort study of the police forces (officers and staff) in mainland Great Britain to investigate long-term health effects associated with use of the TETRA radio system.³² The Airwave Study obtained ethical approval from the National Health Service Multi-site Research Ethics Committee (MREC/13/NW/0588). Airwave participants who consented to be approached for recruitment to subsequent studies, who reside in London and Cambridgeshire, and who are identified eligible based on cardiometabolic risk factors measured at baseline will be approached.
- If necessary, we will extend our recruitment strategy to advertise at waiting rooms of local GP practises and/or direct recruitment via GPs.
- When the study runs at the proposed new location, the Cambridge Epidemiology & Clinical Trials Unit, we aim to use the local Eastern CRN to recruit volunteers via searches of GP patient databases in Cambridge. Posters and adverts will be used if the GP surgeries does not create enough interest.

4.2 Pre-randomisation evaluations

The screening phase to assess suitability for the study consists of a short screening questionnaire telephone interview and a consent/screening visit. Details of procedures are described in the Study methodology section and briefly presented here:

1. **Screening questionnaire/interview:** Respondents will be invited to complete and return by mail the participant information sheet and a screening questionnaire to assess suitability. If preferred, the screening questionnaire can be done by telephone interview. Eligible participants who wish to continue the enrolment process will be invited to attend the Cambridge Epidemiology & Clinical Trials Unit testing sites for a consent/screening visit.
2. **Consent/screening visit:** After receiving consent information and signing the informed consent the following assessments will be done to assess eligibility: general health and lifestyle questionnaire, automated office BP, and anthropometrics and body composition. The researchers will assess the results of both screening tests and will decide if the potential participant can enter the study. The participant will be asked to complete food diaries for 3 days (3 week and 1 weekend days) and a salt intake questionnaire in between visits to assess habitual dietary patterns. Eligible participants will be enrolled and randomly allocated to one of the intervention sequences. In the event of any abnormalities of test results, the participant will be informed and advised to discuss their results with their GP.

Inclusion and exclusion criteria

To limit potential confounding or misleading results, volunteers will be recruited according to inclusion and exclusion criteria as outlined in Table 4.

4.2. Randomisation

If eligible, the participant will be enrolled and randomly allocated to one of the intervention sequences. Randomisation will be carried out by an independent statistician.

4.3. Withdrawal criteria

The safety of the study participants takes priority. Any significant adverse event (as assessed by the researchers) will halt the study and the ethics committee and sponsor will be informed as per standard protocol. All adverse events will be recorded and investigators will review each adverse event as it arises. In addition, participants will be free to withdraw at any time and are not required to give a reason.

Table 4. Inclusion and exclusion criteria

Inclusion criteria:	
Age	40 to 65 years
Automated office systolic BP	Average systolic BP of 125-160 mmHg at 2 measurements separated by >30 min
Antihypertensive medication use	No use less than 3 weeks before screening
Apparently healthy condition	No reported current or previous diabetes mellitus, (secondary) hypertension, or metabolic, cardiovascular, renal, liver, thyroid, gastrointestinal diseases
Body Mass Index	20 to 35 kg/m ²
Smoking status	Non-smoker (not smoked within last 6 months)
Low habitual fruits and vegetable intake	Average fruits and vegetables intake of <4 portions per day (UK average, 40-65 yr) or willing to reduce habitual daily fruit and vegetable intake ≤2 weeks before enrollment
Exclusion criteria:	
Use of other medications	Any medications likely to interfere with energy metabolism, appetite regulation and hormonal balance, including inflammatory drugs or steroids, antibiotics, androgens, phenytoin, erythromycin or thyroid hormones and use of antibiotics.
Alcohol intake	> 21 units per week (females) or >28 units per week (male) and not willing to limit alcohol intake to maximum 1 unit/day ≤2 weeks before and during enrollment
Physical activity	≥10 h/week of moderate to vigorous physical activity
Recent weight loss or gain	≥3 kg in the preceding 3 months
Use of dietary supplements	Unwillingness to stop supplement use ≥2 weeks before enrollment and during intervention
Other medical factors	Pregnancy or lactation
Intervention specific factors	Unable or unwilling to consume provided diets during the intervention Unsufficient storage space for provided diets Food sensitivities or vegetarian/vegan diet by choice Participation in another intervention study at the same time Living >15 miles from the Cambridge Epidemiology & Clinical Trials Unit testing sites, or not willing to travel more than 15 miles No signed informed consent

5. ADVERSE EVENTS

5.1. Definitions

Adverse Event (AE): Any untoward medical occurrence in a patient or clinical study subject.

Serious Adverse Event (SAE): Any untoward and unexpected medical occurrence that:

- results in death

- is life- threatening – refers to an event in which the subject was at risk of death at the time of the event; it does not refer to an event which hypothetically might have caused death if it was more severe.
- requires hospitalisation, or prolongation of existing inpatients' hospitalisation.
- results in persistent or significant disability or incapacity
- is a congenital abnormality or birth defect

Medical judgement should be exercised in deciding whether an AE is serious in other situations. Important AEs that are not immediately life threatening or do not result in death or hospitalisation but may jeopardise

the subject or may require intervention to prevent one of the other outcomes listed in the definition above, should also be considered serious.

5.2. Reporting procedures

All adverse events should be reported. Depending on the nature of the event the reporting procedures below should be followed. Any questions concerning adverse event reporting should be directed to the Chief Investigator in the first instance.

Non-serious AEs

All such events, whether expected or not, should be recorded.

Serious AEs (SEAs)

An SAE form should be completed and faxed to the Chief Investigator within 24 h. However, relapse, death and hospitalisations for elective treatment of a pre-existing condition do not need reporting as SAEs.

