5.3. Referral procedures

All SAEs should be reported to the Research Ethics Committee where in the opinion of the Chief Investigator the event was:

- 'related', i.e. resulted from the administration of any of the research procedures; and
- 'unexpected', i.e. an event that is not listed in the protocol as an expected occurrence.

Reports of related and unexpected SAEs should be submitted within 15 days of the Chief Investigator becoming aware of the event, using the NRES SAE form.

Local investigators should report any SAEs to the sponsor and their Local Research Ethics Committee and/or Research and Development Office.

**Contact details for reporting SAEs, for attention of
[name] [name] –
[contact] [contact]
Email: [contact]
(Mon to Fri 09.00- 17.00)**

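### Protocol 5.1 makes death a criterion for a serious adverse event, but 5.2 exempts death from SAE reporting, so it is unclear whether a fatal event needs the 24 h form and the 5.3 reports

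*Protocol*

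**What the plan says.** Protocol 5.1 (Definitions) opens the SAE definition with "Any untoward and unexpected medical occurrence that" and lists five criteria. The first is "results in death". The second, life-threatening, "refers to an event in which the subject was at risk of death at the time of the event". The others are hospitalisation or its prolongation, disability or incapacity, and congenital abnormality. A closing paragraph leaves room for medical judgement in other situations.

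Protocol 5.2 (Reporting procedures) begins with a general rule, "All adverse events should be reported", and adds: "Any questions concerning adverse event reporting should be directed to the Chief Investigator in the first instance". For serious events it says "An SAE form should be completed and faxed to the Chief Investigator within 24 h". The exemption follows at once: "However, relapse, death and hospitalisations for elective treatment of a pre-existing condition do not need reporting as SAEs".

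Protocol 5.3 (Referral procedures) has two onward routes. SAEs that the Chief Investigator considers related and unexpected go to the Research Ethics Committee "within 15 days of the Chief Investigator becoming aware of the event". Separately, local investigators report any SAE to the sponsor and to the local ethics committee and/or R&D office, with no time limit given.

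Protocol 4.3 (Withdrawal criteria) says that an adverse event the researchers assess as significant halts the study and that the ethics committee and sponsor are informed. It also has every adverse event recorded and reviewed as it arises.

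SAP 5.3 (Safety data) tabulates adverse events by randomised sequence, overall and split into non-serious and serious. It has no separate rule for deaths.

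**The concern.** Sections 5.1 and 5.2 give opposite answers for the same event. The exemption of death in 5.2 is not limited by cause, relatedness or expectedness. Taken literally, an event that put a participant at risk of death needs the 24 h form, while the death itself does not need reporting as an SAE.

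Three things are at stake: the form and its 24 h limit; the 5.3 reports, both of which are triggered by an event being an SAE; and, less directly, whether a fatal event is placed in the serious column of the SAP 5.3 table. The population sharpens the point. Participants are apparently healthy and Protocol Table 4 excludes major disease, so nothing in the protocol suggests a class of deaths that could sensibly be left out.

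**Working it through.** The point is a comparison of text; the plan has no figure of its own to reproduce.

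**Step 1. Classification against action.** Under 5.1, an untoward and unexpected occurrence that ends in death is an SAE. Under 5.2, an SAE needs the form within 24 h, but death need not be reported as one. Of the five criteria in 5.1, death is the only one that 5.2 exempts by name.

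**Step 2. Can the sentence be read so that the conflict disappears?**

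- *Plain reading:* death is a separate item in a list of three. Every death is exempt, which contradicts 5.1 directly.
- *Narrow reading:* the closing phrase about elective treatment of a pre-existing condition limits all three items. The grammar does not favour this, because the phrase attaches to hospitalisations. Even so read, an unexpected death in that setting would be an SAE under 5.1 and exempt under 5.2. The conflict is smaller but remains.
- *Only expected deaths are meant:* 5.2 does not say so. Section 5.3 treats an event as unexpected if the protocol does not list it as an expected occurrence, and the supplied protocol text lists none.

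**Step 3. Which fatal events could lose the form?** The 5.1 criteria overlap.

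| Course of the event | Other 5.1 criterion met? | Form still required by that route? |
|---|---|---|
| Admitted (not electively), then dies | Hospitalisation; usually life-threatening too | Yes, unless staff read 5.2 as exempting the whole event |
| Life-threatening event seen before death, no admission | Life-threatening | Yes, with the same proviso |
| Found dead, course not observed | Arguable | Unclear; death is the only plain criterion |

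The form is therefore most exposed in the last row. In the first two it depends on how staff read 5.2.

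**Step 4. Do other provisions restore the step?**

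| Provision | What it secures | SAE form or 24 h limit? |
|---|---|---|
| 5.2 general rule | Every adverse event is reported | No |
| 5.2 queries to the Chief Investigator | Staff who notice the conflict can ask | No |
| 4.3 recording and review | Each event is seen by investigators | No |
| 4.3 significant event | Study halts; ethics committee and sponsor informed | No; depends on the researchers' assessment |

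**Step 5. Downstream.** Section 5.3 does not say whether an event exempted under 5.2 is still an SAE for either of its routes. Section 5 contains two time limits: the 24 h limit is in conflict for a death, and whether the 15-day limit applies is unclear. In SAP 5.3 the natural reading is that seriousness follows 5.1, so a fatal event would be counted as serious, but neither document says so.

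**Step 6. How likely is the case to arise?** Inputs: 36 participants (Protocol section 6) and 9 weeks each (Protocol section 1, Duration).

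- Exposure: 36 × 9 = 324 person-weeks; 324 × 7 = 2,268 days; 2,268 / 365.25 = 6.21 person-years.
- Assumed mortality, not given in the documents: 1 to 5 deaths per 1,000 person-years.
- Expected deaths: 6.21 × 0.001 = 0.006 to 6.21 × 0.005 = 0.031.
- Chance of at least one: 1 − exp(−0.0062) = 0.6% to 1 − exp(−0.0310) = 3.1%.

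**The case against.** The strongest reply is that little is actually lost. Section 5.2 exempts death; it does not exempt every event that ends in death. A fatal stroke or infarction would normally also be life-threatening or lead to admission, and those criteria are not exempt apart from elective admissions. A death in a healthy volunteer would almost certainly be judged significant under 4.3, so the study would halt and the ethics committee and sponsor would be told. The exemption also does not alter the 5.1 definition, so a fatal event would already be counted as serious in the SAP table.

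Most of this stands. It rules out two stronger conclusions that a reader might draw. The first is that deaths would go unreported: the documents do not support this, because the general rule in 5.2 and the recording, review and halt provisions in 4.3 all still apply. The second is that the 24 h form is certainly lost for every fatal event: the overlap among the 5.1 criteria and the narrow reading of the exemption both prevent that.

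The reply does not remove the conflict. No other provision requires the form or its time limit, and staff may reasonably take 5.2 to exempt the whole event.

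A further reply is that *relapse*, in the same sentence, raises a similar question if it leads to an unexpected admission. The word has no evident meaning in this population, since the protocol defines no condition that could relapse. It can be looked at when the sentence is revised, but the direct contradiction with a named criterion concerns death.

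**Conclusion.** The 5.2 exemption is wrong as written. It conflicts with 5.1 on whether death is reported as an SAE, and so leaves open whether the 24 h form and the 5.3 routes apply. The omission of the form is what the plain wording permits; it is a possible loss, not a demonstrated one.

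The practical impact is low. The chance that any death occurs in the planned exposure is roughly 0.6% to 3.1%, which rests wholly on the assumed mortality range. No efficacy analysis is affected. A reader might also infer that the safety table is unreliable or that all adverse event records need auditing. The documents do not support either: the defect concerns deaths only, and 5.1 still defines them as serious.

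**What to change.** Reconcile the exemption sentence in Protocol 5.2 with 5.1 by removing *death* from it. Add a sentence stating that an event meeting 5.1 by death counts as an SAE for three purposes:

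- the 24 h form in 5.2;
- the routes in 5.3, keeping the existing restriction of ethics reports to related and unexpected events;
- the serious/non-serious split in SAP 5.3.

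The cost is a small wording amendment, which under Protocol section 7 (Ethics approval) needs sponsor, ethics and Trust R&D approval.

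Timing limits its value. The SAP, signed on 4 March 2022, already refers in 5.2.1 to 6 individuals whose sequences were mixed up, so randomisation had begun; the documents do not say whether follow-up is complete. If it is, the amendment adds little. The useful step is then to confirm whether any participant died and, if so, that the event was handled and counted as an SAE. With at most 36 planned participants, that is a brief check.
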